#### 10 STUDY PROCEDURES

#### 10.1 Overview

Individuals ages 45 to 49 who are at average risk for development of CRC will be invited to participate in the study. 914 subjects are targeted to enroll. Subjects providing written informed consent to participate in the study will complete the mt-sDNA test (Cologuard) followed by a screening colonoscopy which should be completed within approximately 60 days of enrollment. Subjects may also choose to consent to 2018-10B and provide a blood sample at the time of enrollment.

Refer to Appendix 1.0 – Study Schema and Appendix 2.0 – Schedule of Activities

#### 10.2 Enrollment

Subjects are considered enrolled once written informed consent is obtained and subject eligibility confirmed.

#### 10.3 Blood Sample Collection

If the subject also consents to 2018-10B, approximately 40 mL of peripheral blood will be collected from the subject. Blood sample collection should occur on the same day as enrollment. The Sponsor will provide the site with blood sample collection, processing, and shipping procedures.

#### 10.4 Stool Sample Collection

Enrolled subjects will complete the mt-sDNA test (Cologuard) prior to bowel preparation for the colonoscopy procedure. Subjects enrolled into the study will be provided with a Stool Collection Kit. Stool samples must be collected prior to initiation of bowel preparation for the colonoscopy procedure. Stool samples will be collected by following the instructions provided. Instructions for kit return are provided to the subject with the Stool Collection Kit.

#### Master Clinical Protocol 2018-10

The shipment and arrival of the Stool Collection Kit at Exact Sciences Laboratories will be tracked. Once the sample arrives at Exact Sciences Laboratories, it will be inspected for acceptability per the specifications outlined in the Cologuard Instructions for Use. If the stool sample is not collected according to the instructions for use or damaged in a way that compromises the specimen, a repeat sample collection may be requested if the collection can occur prior to the initiation of bowel preparation for the scheduled colonoscopy. The site will be asked to contact the subject to request another stool specimen. At that time, another stool collection kit will be dispensed to the subject by the site.

#### 10.5 Sample Assays

Assay results will be recorded as 'Positive', 'Negative', 'Sample Could Not Be Processed', or 'No Result Obtained.' If there are no valid results, a repeat test may be requested. Repeat stool sample requests will be sent to the site. Repeat stool sample collection must occur prior to bowel preparation for the colonoscopy procedure. If a valid stool sample result cannot be obtained for a subject after two (2) attempts, the subject will be withdrawn and may be replaced.

The mt-sDNA test (Cologuard) result will not be provided to investigators for clinical management of study subjects. All mt-sDNA test results will remain blinded to investigators and study subjects.

#### 10.6 Colonoscopy and Histopathology

Every subject will undergo a screening colonoscopy after completing a mt-sDNA test (Cologuard) test. Colonoscopies should occur as soon as possible following informed consent and stool collection. Subjects who have poor bowel preparation and will not repeat the procedure or subjects who do not complete a colonoscopy should be withdrawn and may be replaced. Bowel preparation procedures and colonoscopy will be performed following the usual practice at each clinical site. Personnel performing the colonoscopy and producing the resulting report and the personnel performing the histopathological review of tissue will remain blinded to the results of the mt-sDNA test (Cologuard) result.

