# exact sciences

#### **Document Type:**

#### Master Clinical Protocol 2018-10

#### 9.3 Subject Withdrawal

Subjects may be withdrawn from the study by any of the following mechanisms:

- 1. Voluntary withdrawal of consent to participate by the subject at any time during the study.
- 2. Determination by the clinical investigator that it is in the best interest of the subject.
- 3. Determination by the Sponsor it is in the best interest of the subject or study.
- 4. Stool sample not provided within 30 days of enrollment.
- 5. Colonoscopy procedure is not done.

All data available from enrollment to subject withdrawal will be collected unless the subject withdraws consent from the study. Data for all study visits will be collected for subjects who discontinue participation but who do not withdraw consent. Withdrawal of consent must be documented by site personnel in the subject source record.

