#### 10.6.1 Colonoscopy Procedure

Bowel preparation procedures and colonoscopy will be performed following standard of care at each clinical site. The colonoscopist will record the quality of the bowel preparation (after washing/suctioning) as follows:

- Excellent: minimal fecal residue and liquid, small volume of liquid easily aspirated, <5% of colonic surface covered;
- **Good**: small amounts of fecal residue, volume of clear liquid covering 5-25% of surface, easily aspirated;
- Fair: moderate amounts of fecal residue; stool limited examination but >90% could be examined: or
- **Poor**: large amounts of stool, <90% of surface could be examined.

Cecal intubation will be documented with photographic evidence and/or documentation of cecal intubation; and colonoscope withdrawal time will be recorded. Withdrawal time is defined as the time from cecal identification to the time when the colonoscope is withdrawn across the anus (Barclay, Vicari, Doughty, *et al*, 2006.).

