#### Master Clinical Protocol 2018-10

A bowel preparation considered excellent, good, or fair will be acceptable. Subjects with no findings on the colonoscopy, and no photographic evidence of cecal intubation or no documentation of cecal intubation in the report, will be deemed to have a failed colonoscopy. These subjects will be deemed to be unevaluable and therefore will be excluded from analysis of the primary and secondary endpoints.

Those subjects determined to have had a poor bowel preparation (after washing/suctioning) may repeat the colonoscopy again if the Investigator feels this is in the best interest for the subject. The subject may repeat the colonoscopy procedure. A repeat stool specimen is not required.

A completed colonoscopy procedure will be considered and defined as: reaching the cecum (or) reaching the junction between the small and large intestine (in the event the cecum has been resected).

A colonoscopy wherein a CRC or AA was identified will be included in the analyses regardless of any limiting factors experienced during the colonoscopy.

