#### 12.2 Primary Endpoint

The primary endpoint of this study is the specificity of the mt-sDNA test (Cologuard) in the 45-49 age group in an average risk population, using colonoscopy with histopathology (when required) as the reference method. The primary analysis requires the one-sided 97.5% lower bound of the specificity of Cologuard to exceed 85.0%.

The primary endpoint of this study is to confirm the specificity of the mt-sDNA test (Cologuard) in the 45-49 age group in an average risk population. Specificity will be determined by comparing the mt-sDNA test result to the results of optical colonoscopic examination and confirmation of the colonoscopic findings by histopathology, if appropriate.

Possible categories of colonoscopic findings are as follows:

- 1. CRC, all stages (I-IV);
- 2. Advanced adenoma, including the following subcategories:
  - 2.1 Adenoma with carcinoma in situ or high-grade dysplasia, any size
  - 2.2 Adenoma, villous growth pattern (≥ 25%), any size
  - 2.3 Adenoma > 1.0 cm in size, or
  - 2.4 serrated lesion, > 1.0 cm in size;
- 3. 1 or 2 adenoma(s), > 5 mm in size, or < 10 mm/1.0 cm size, non-advanced;
- 4. > 3 adenomas, < 10 mm in size, non-advanced;
- 5. 1 or 2 adenoma(s), < 5 mm in size, non-advanced;
- 6. Negative no neoplastic findings, including the following subcategories:
  - 6.1 Negative, no colorectal neoplasia upon histopathological review
  - 6.2 No findings on colonoscopy, no biopsy(s) taken

Subjects with colonoscopic findings in categories 3-6 above will be included in the specificity analysis as negative outcomes for the primary endpoint calculation. Thus, specificity to advanced neoplasia (AN) will be calculated for the primary endpoint evaluation. The colonoscopically 'negative' population (category 6) will include those subjects with a colonoscopy showing no findings of colorectal neoplasia, non-neoplastic disease, and/or hyperplastic polyps  $\leq$  1 cm in diameter.

Subjects with no findings on the colonoscopy, no photographic evidence of cecal intubation and no documentation of cecal intubation in the report, will be deemed to be unevaluable and therefore will be excluded from all analyses. Subjects found to have occult inflammatory bowel disease (IBD) on

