#### Master Clinical Protocol 2018-10

#### APPENDIX 3.0 – GUIDELINES FOR COLONOSCOPY

Bowel preparation procedures and post-enrollment colonoscopy will be performed following the established standard of practice at each clinical site. Results of the colonoscopy examination will be collected.

The quality of the colonoscopy bowel prep must be documented after washing/suctioning as follows:

- Excellent minimal fecal residue and liquid, small volume of liquid easily aspirated, <5% of colonic surface covered;
- Good small amounts of fecal residue, volume of clear liquid covering 5-25% of surface, easily aspirated;
- Fair moderate amounts of fecal residue; stool limited examination but >90% could be examined;
- **Poor** large amounts of stool, <90% of surface could be examined.

Subjects with negative colonoscopy results and a poor bowel preparation will not be included in endpoint analyses.

Cecal intubation must be documented with photographic evidence and/or documentation of cecal intubation. Subjects with a negative colonoscopy will not be included in endpoint analyses if no documentation of cecal intubation is present.

For all subjects with histopathological findings of CRC (Category 1.0) or precursor lesions (Category 2.0), neither the quality of bowel preparation nor documentation of cecal intubation need to be present for the subject to be included in endpoint analyses.

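### Limited colonoscopies are handled by conflicting rules: Protocol 10.6 withdraws subjects whom other sections analyse, and the SAP's ITS set counts some partly examined colons as disease-negative

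*Protocol*

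**What the plan says.** **Withdrawal.** Under Protocol 10.6, subjects with poor preparation who "will not repeat the procedure or subjects who do not complete a colonoscopy should be withdrawn and may be replaced". Poor preparation is defined in 10.6.1 as "large amounts of stool, <90% of surface could be examined". The general withdrawal list in Protocol 9.3 is narrower and names only "Colonoscopy procedure is not done".

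**Inclusion of CRC and AA.** Protocol 10.6.1 states: "A colonoscopy wherein a CRC or AA was identified will be included in the analyses regardless of any limiting factors experienced during the colonoscopy". Appendix 3 agrees: for these subjects "neither the quality of bowel preparation nor documentation of cecal intubation need to be present for the subject to be included in endpoint analyses". SAP 2.1 classes such an examination as complete, and SAP 2.4 repeats that it is analysed.

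**Exclusion of inadequate examinations.** Protocol 10.6.1 and 12.2 exclude subjects with no findings whose cecal intubation is not evidenced. Appendix 3 adds: "Subjects with negative colonoscopy results and a poor bowel preparation will not be included in endpoint analyses". None of these sentences names categories 3 to 5.

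**Specificity denominator.** Protocol 12.2: "Subjects with colonoscopic findings in categories 3-6 above will be included in the specificity analysis as negative outcomes".

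**SAP populations.** SAP 2.2 runs all effectiveness analyses in ITS, with PP as confirmation. Under SAP 2.6.2, a valid test plus a reportable colonoscopy is enough for ITS, and SAP 2.1 defines reportable as attempted with a report available. SAP 2.8.1 removes no-findings subjects without cecal documentation from PP only.

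**The concern.** A subject can be called free of advanced neoplasia only if the colon was adequately seen. If the examination stopped short of the cecum, or much of the surface was hidden, an AA may have been missed. A positive stool test caused by that lesion is then scored as a false positive.

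Two things are at stake. The first is the primary denominator: the Protocol and SAP do not describe the same set of disease-negative subjects, and specificity is the only primary endpoint. The sample was raised from 225 to 731 for precision alone, so who makes up the 731 should be settled. The second is the small AA group behind the exploratory sensitivity estimate. The text used to withdraw subjects and the text used to analyse them give different answers for an AA found in a limited examination.

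**Working it through.** **1. The rules applied to each kind of limited examination** (valid test assumed; for PP, also a usable test and no major deviation).

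| Finding | Protocol | SAP ITS | SAP PP |
|---|---|---|---|
| CRC or AA | 10.6 withdraws; 10.6.1 and Appendix 3 include | In | In (counts as complete) |
| Category 3-5, cecum not reached | 10.6 withdraws; exclusions in 10.6.1 and 12.2 are worded for no findings only | In, disease-negative | Out |
| Category 3-5, cecum reached, poor preparation | 10.6 withdraws if not repeated; Appendix 3 excludes only if its term negative covers categories 3-5 | In, disease-negative | Can be in |
| No findings, no cecal documentation | 12.2 excludes from all analyses | In, disease-negative | Out |
| No findings, cecum reached, poor preparation | Appendix 3 excludes | In, disease-negative | Can be in |

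The ITS definition does not mention withdrawal status, so a subject withdrawn under 10.6 can still meet it. The last column follows because the SAP's definition of a complete colonoscopy has no preparation criterion.

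The word negative is used in two ways. Protocol 12.2 ties the colonoscopically negative population to category 6, but also treats categories 3-6 as negative outcomes, and 12.3.1 calls the whole specificity sample colonoscopy negatives.

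The triggers differ too: Protocol 9.3 and SAP 2.7.2 refer to a colonoscopy not done, Protocol 9.4 to one not completed, and Protocol 10.6 adds poor preparation.

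**2. The plan's own figures** (Protocol 12.2 and 12.3).
- Exact one-sided test, null 85.0%, alternative 92.2%, alpha 0.025, n = 731: success needs at least 641 negative tests, attained alpha 0.0216, power 99.999% (stated >99.99%).
- Clopper-Pearson interval at 92.2%, n = 731: 90.0% to 94.0%.
- 731/0.8 = 914 enrolled; 731 × 3.92% = 28.7, about 29 AA subjects.

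**3. Size.** The documents give no rate of limited examinations. Assumed: 731 + 29 = 760 examinations, 3-8% limited, 30-45% of those with only a non-advanced adenoma.
- Category 3-5 subjects affected: 760 × 0.03 × 0.30 = 6.8 to 760 × 0.08 × 0.45 = 27.4, so about 7 to 27.
- AA subjects under the withdraw-versus-include conflict: 29 × 0.03 = 0.9 to 29 × 0.08 = 2.3.
- Missed AA among 27 subjects, taking the plan's 3.92% prevalence as the missed rate: 27 × 0.0392 = 1.06. If every one tests positive, the effect is at most 1.06/731 = 0.145 point. Net of the 7.8% false-positive rate already expected, it is 1.06 × (1 − 0.078)/731 = 0.13 point.
- Direction: a missed AA lowers observed specificity whenever its chance of a positive test exceeds 7.8%.

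**4. Wider bound, all limited examinations whatever was found.** This also covers the no-findings rows of the table. At the upper assumed rate, 760 × 0.08 = 61 examinations. The rows below bracket that, with 3.92% missed AA and all testing positive.

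| Limited share of 731 | Missed AA | Expected specificity | Power |
|---|---|---|---|
| 5% | 1.43 | 92.02% | 99.998% |
| 10% | 2.87 | 91.84% | 99.995% |
| 20% | 5.73 | 91.48% | 99.98% |

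**5. Removing them instead, without replacement.** A loss of 5% leaves n = 694 and an interval of 89.9% to 94.1%. A loss of 20% leaves n = 585, an interval of 89.7% to 94.2%, and power of 99.98%.

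**The case against.** Several points on the other side stand, and they rule out stronger readings that a reader might infer.

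- *That every such subject is replaced, or that AA cases drop out of the analysis.* Replacement under 10.6 is optional, and replacing a subject does not delete the one replaced. SAP 2.1 and 2.4 keep CRC and AA subjects.
- *That pathology arriving after withdrawal is lost.* Protocol 9.3 goes on to say that visit data are collected from subjects who discontinue without withdrawing consent. Protocol 10.6.2 and Appendix 4 expect surgical and histopathology reports to be available.
- *That the Protocol expressly keeps small-adenoma subjects after an inadequate examination.* It does not. Their place follows from silence on categories 3-5, the double use of negative, and the SAP's ITS rule. If negative in Appendix 3 means categories 3-6, the poor-preparation case is already excluded on the Protocol side.
- *That each site would produce its own denominator.* SAP 2.6 has the CRO review the data that decide population membership.
- *That the primary conclusion is at risk.* The calculations do not support this.

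It can also be said that SAP 2.6.3 leaves ITS exclusion rules to be set before database lock, and that SAP 2.9.1 asks for the colonoscopy to be complete before lock. The former is a promise, not a rule. The latter reads as timing, because the exclusion attached to it is for examinations that are not reportable. Protocol 12 lets the SAP modify the plan, but requires an amendment for major changes to the primary endpoint definition or its analysis, and SAP 5 reports no changes.

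**Conclusion.** The point holds as one of population definition. Protocol 10.6 conflicts on its face with 10.6.1, Appendix 3 and SAP 2.1 and 2.4 for CRC and AA subjects. The SAP's ITS rule, followed as written, puts partly examined colons into the primary specificity as disease-negative. For no-findings subjects without cecal documentation, this directly contradicts Protocol 12.2. PP is only a partial check, because poorly prepared examinations that reach the cecum can enter it.

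The numerical effect is small. For the 7 to 27 small-adenoma subjects it is at most about 0.15 point of specificity. With no-findings subjects added, it stays below 0.4 point up to a 10% share of limited examinations. It works against the success claim, and power stays at about 99.98% or more even at a 20% share. Perhaps 1 to 2 of about 29 AA subjects are caught by the withdrawal conflict, in an exploratory estimate. All of this rests on assumed rates of limited examinations and small findings, and on using 3.92% as the missed-AA rate.

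**What to change.** Reconcile Protocol 9.3, 9.4, 10.6, 12.2 and Appendix 3 with SAP 2.1, 2.6.2, 2.6.3, 2.7.2 and 2.8.1 through one analysis-evaluability rule, worded identically in both documents:

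- (a) A subject with histologically confirmed CRC or AA is retained and analysed, whatever the limits of the examination.
- (b) A subject in categories 3-6 counts in the primary specificity analysis only if the examination reached the cecum, or the equivalent defined in Protocol 10.6.1, with preparation that 10.6.1 calls acceptable. The same preparation criterion applies in PP.
- (c) The ITS set as now defined, with a reportable colonoscopy, is kept as a sensitivity analysis.

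Name the categories instead of writing negative, and use one trigger for withdrawal and replacement throughout. Since the primary denominator changes, record this in a protocol amendment and in SAP 5.

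The cost is wording and the loss of a few limited examinations from the denominator. The rule governs who is analysed. Whether an examination is repeated stays as the Protocol has it.

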#### 10.6.1 Colonoscopy Procedure

Bowel preparation procedures and colonoscopy will be performed following standard of care at each clinical site. The colonoscopist will record the quality of the bowel preparation (after washing/suctioning) as follows:

- Excellent: minimal fecal residue and liquid, small volume of liquid easily aspirated, <5% of colonic surface covered;
- **Good**: small amounts of fecal residue, volume of clear liquid covering 5-25% of surface, easily aspirated;
- Fair: moderate amounts of fecal residue; stool limited examination but >90% could be examined: or
- **Poor**: large amounts of stool, <90% of surface could be examined.

Cecal intubation will be documented with photographic evidence and/or documentation of cecal intubation; and colonoscope withdrawal time will be recorded. Withdrawal time is defined as the time from cecal identification to the time when the colonoscope is withdrawn across the anus (Barclay, Vicari, Doughty, *et al*, 2006.).

#### Master Clinical Protocol 2018-10

A bowel preparation considered excellent, good, or fair will be acceptable. Subjects with no findings on the colonoscopy, and no photographic evidence of cecal intubation or no documentation of cecal intubation in the report, will be deemed to have a failed colonoscopy. These subjects will be deemed to be unevaluable and therefore will be excluded from analysis of the primary and secondary endpoints.

Those subjects determined to have had a poor bowel preparation (after washing/suctioning) may repeat the colonoscopy again if the Investigator feels this is in the best interest for the subject. The subject may repeat the colonoscopy procedure. A repeat stool specimen is not required.

A completed colonoscopy procedure will be considered and defined as: reaching the cecum (or) reaching the junction between the small and large intestine (in the event the cecum has been resected).

A colonoscopy wherein a CRC or AA was identified will be included in the analyses regardless of any limiting factors experienced during the colonoscopy.

#### 10.6.2 Colonoscopy and Histopathology Reports

Colonoscopy findings will be recorded on the colonoscopy reports per site-specific standard of practice. Histopathology interpretation of tissue samples will be conducted according to each of the clinical site's local histopathology practice provider(s) as used for daily patient management.

Subjects who have lesions identified by colonoscopy that are neither biopsied initially nor excised subsequently or that are lost during lesion retrieval and, therefore, not submitted for histopathologic analysis, will be identified by the sites, and the colonoscopy report will be sent to the study central pathologist(s) for review. Because of the absence of confirmatory histopathologic diagnosis, these subjects will be excluded from the study based on the fact that they cannot be categorized for the study analysis.

The sites will grant independent central pathologist(s) access to colonoscopy, surgical, and histopathological reports by providing them a copy of those reports. All protected health information on the documents will be removed before release to the central pathologist(s). The study-specific subject identification number will be used to identify colonoscopy reports and applicable histopathology reports submitted to the central pathologist(s).

Histopathological results will be categorized as defined in **Appendix 4**. For subjects that undergo surgical removal of CRC and/or non-CRC lesions, an excisional surgical pathology report should be available. To ensure diagnostic accuracy, investigative sites with subjects diagnosed with CRCs or AAs may be required to provide representative histology slides for review by a central pathologist. When the central pathologist histopathology result differs from the local histopathology result, the results will be adjudicated with a review and interpretation by a second central pathologist.

Patient management will be conducted locally at each investigative site based upon colonoscopy outcomes and the histopathology results reported by the local pathology lab. In the event that the centralized histopathology laboratory assigns a higher-grade histology result than the local histopathology laboratory, the Investigator will be notified. The Investigator should maintain the central pathology results with the subject's source records. The central pathology laboratory results may not be available prior to the subsequent treatment of the subject.

